If discontinuation of study treatment occurs, the patient should NOT be considered withdrawn from the study. The patient should continue to return to the clinic for the scheduled visits in the respective treatment period. If the patient decides to leave the study, a study treatment discontinuation visit must occur as soon as possible after actual discontinuation of the study drug. Treatment discontinuation visit assessments detailed in the "unscheduled treatment discontinuation visit" (TD) in [Table 6-1](#) and [Table 6-2](#) should be completed and recorded in the eCRF. The investigator must determine the primary reason for the patient's premature discontinuation of study treatment and record this information on the Dosage Administration eCRF.

Patients who discontinue after having received at least one VAY736 administration and who do not complete the visits in the respective treatment period should return for the long-term safety follow up period 4. In period 4, visits are scheduled as outlined in [Table 5-3](#) below

Table 5-3 Outline of visit frequency in period 4

Visit frequency	TD period 2	TD period 3	No. of visits
Every 4 weeks	week 24 -week 40	week 52 - week 68	4 visits
Every 8 weeks	week 40 - week 56	week 68 - week 84	2 visits
Every 12 weeks	week 56 - week 80	week 84 - week 108	2 visits
Every 24 weeks	week 80- week 128	week 108 - week 156	2 visits

TD = Study treatment discontinuation

The End-of-Study visit will include study completion evaluations followed by discharge from the study. Patients who discontinue during the safety follow up period will be asked to complete the end of study visit. For patients who are lost to follow-up (i.e., those patients whose status is unclear because they fail to appear for study visits without stating an intention to withdraw), the investigator should show “due diligence” by documenting in the source documents steps taken to contact the patient, e.g., dates of telephone calls, registered letters, etc.

The investigator must also contact the IRT to register the patient’s discontinuation from study treatment.

If study drug discontinuation occurs because treatment code has been broken, please refer to [Section 5.5.9](#).

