ESSDAI		x	x	x	x	x	x		x	
Salivary flow (stimulated and unstimulated)		x		x		x		x		
Saliva sample		x		x		x		x		
Local ECG			x					x		
Re-randomization		S ³								
Dosage administration record		x	x	x	x	x	x			
Pre-medication		x								
Contact IRT		S	S	S	S	S	S		S	
Adverse events		x	x	x	x	x	x		x	AEs include both serious and non-serious events
Renal/liver event monitoring		x	x	x	x	x	x		x	
Concomitant medications		x	x	x	x	x	x		x	
Period completion/disposition form										x
ESSPRI, FACIT-F, SF-36, PaGA, patient diary ⁴		x	x	x	x	x	x	x	x	4Diary is to be completed weekly by patient

³IRT will confirm if patient will be treated in period 3 but not notify whether patient was re-randomized

Re-randomization

Dosage administration record

Pre-medication

Contact IRT

Adverse events

Renal/liver event monitoring

Concomitant medications

Period completion/disposition form

ESSPRI, FACIT-F, SF-36, PaGA, patient diary⁴

Period	Period 3: Extended Treatment							Notes
	201	202	203	204	205	206	207	
Visit								
Day	168	196	224	252	280	308	336	364
Week	24	28	32	36	40	44	48	52
Hematology and biochemistry								
Serum pregnancy	x	x	x	x	x	x	x	x
Urinalysis	x	x	x	x	x	x	x	x
IgG, IgM	x	x	x	x	x	x	x	x
Pre-dose PK sample		x	x	x	x	x	x	
Post-dose PK sample							x	
Immunogenicity				x		x		

TD = Study treatment discontinuation; If patient withdraws consent (as per definition) and will not enter period 4, assessments from Table 6-3 PSD must be performed as well
 X = assessment to be recorded on clinical data base
 S = assessment to be recorded on source documentation only

Table 6-3 Assessment schedule for study period 4 (safety follow-up period) for all patients

Period 4: Follow-up	Mandatory follow-up visits	Conditional individualized follow-up visits	Mandatory	Notes
Visit	301 302	303 ⁹ 304	305 and 306 308 and 309	399 ¹⁰ / PSD/ (EoS)
Study week for patients who completed period 3 treatment	56 60	64 68	76 and 84 96 , 108¹² and 132	156 ¹¹ ¹² Marks the 1 year follow up time point
Study week for patients who completed period 2 treatment	28 32	36 40	48 and 56 68 , 80¹² and 104	128 ¹¹ ¹² Marks the 1 year follow up time point
Physical exam	S S	S S	S S	S S
Weight, vital signs	x x	x x	x x	x x
ESSDAI	x x	x x	x x	x x
Adverse events	x x	x x	x x	x x
Kidney and liver event monitoring	x x	x x	x x	x x
Concomitant medications	x x	x x	x x	x x
Period completion/disposition form				x
Hematology and biochemistry	x x	x x	x x	x x
IgG, IgM	x x	x x	x x	x x

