### 1.1 Study design

This is a randomized, double-blind, placebo-controlled, multicenter, parallel-group trial in approximately 180 patients with active pSS. The study is divided into 4 study periods:

**Period 1:** A screening period of 4 weeks to assess patient eligibility. Patients can be re-screened only once and no study-related re-screening procedure should be performed prior to written re-consent by the patient.

**Period 2:** At baseline, eligible patients will be randomized to one of three VAY736 dose arms (VAY736 5 mg, 50 mg or 300 mg s.c.) or a placebo arm. Blinded study drug will be administered every four weeks for a 24-week period. Approximately 45 patients will be randomized per treatment group. [REDACTED], randomization will be stratified by:

- baseline ESSDAI score (<10 or  $\geq 10$  based on weighted scores)

[REDACTED]

The primary endpoint will be assessed at the end of period 2 (week 24).

[figure not shown]
Treatment assignment in period 2 will remain double blinded until the end of period 3.

**Period 3:** After week 24 assessments, patients in the VAY736 300 mg arm will be re-randomized in a 1:1 ratio to either continue VAY736 300 mg s.c. every four weeks or switch to [REDACTED] placebo up to week 52. Patients who received placebo during period 2 will be switched to VAY736 150 mg s.c every four weeks up to week 52. Patients who received 5 mg and 50 mg s.c. in period 2 will proceed directly to period 4. Treatment assignment in period 3 will remain double blinded until the end of the study period.

**Period 4:** The safety follow-up period lasts for a minimum of 20 weeks from last dose administration of VAY736, or longer (with reduced visit frequency) [REDACTED] whichever occurs first ([Figure 1-1](#)) ([van Vollenhoven 2012](#); [Emery 2014](#), [Genovese 2008](#)).

Patients who have not yet recovered their B-cell counts two years after last VAY736 dosing, will be discharged from the study and undergo their End of Study (EoS) visit. Patients who will be treated with another immunmodulatory or immunsuppressive treatment (e.g. azathioprine, cyclophosphamide, high dose glucocorticosteroids) after completion of the minimum 20 week safety follow-up period are excluded from further safety follow-up.

The primary efficacy analysis will be performed when all patients have completed the week 24 study visit.

**Figure 1-1** Study design

[figure not shown]

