### **End of Treatment Date (EoT)**

The end of treatment date is the date of EoT disposition on CRF page for patients who complete the study treatment(s) as per protocol, or the date of the last dose plus 27 days if patients early discontinue the treatment. Therefore, the end of treatment date (EoT) in period 2 is defined as below:

- 1) patients who complete period 2 treatment and enter period 4 directly: EoT = the date of period 2 disposition on CRF page
- 2) patients entering period 3: EoT = the date of the first dose in period 3
- 3) patients early discontinue the treatment in Period 2: EoT = the date of the last dose in period 2 plus 27 days .

The end of treatment date (EoT) in period 3 is defined as below:

- 1) patients who complete period 3 treatment: EoT = the date of period 3 disposition on CRF page
- 2) patients early discontinue the treatment in Period 3: EoT = the date of the last dose in period 3 plus 27 days .

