### **Period**

The period 2 starts from the first dose on Day 1 visit; the period 2 end date is the end of treatment date in period 2. The period 3 starts from first dose in period 3; the period 3 end date is defined as the end of treatment date in period 3. The period 4 starts on the day after the end of treatment in period 2/3. Assignment of events to each period will be based on date and time. When time is missing or not reported, the assignment will be based on date only; in that case, events starting on the date of first dose in period 3 will be assigned to the period 3 for those who are entering period 3, or to the safety follow-up period.

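### Protocol Table 5-3 gives early stoppers who leave the treatment-period visits the completers' fixed study weeks, so read literally it delays their scheduled safety checks after last dose

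*Protocol*

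**What the plan says.** **Default for early stoppers (Protocol 5.6.2).** Stopping drug does not end participation: "The patient should continue to return to the clinic for the scheduled visits in the respective treatment period". Patients who follow this default through week 24 or 52 are not at issue.

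**Those who leave the treatment-period visits (Protocol 5.6.2).** Patients with at least one VAY736 dose "who do not complete the visits in the respective treatment period should return for the long-term safety follow up period 4", with visits as in Table 5-3. Section 5.5.6 points permanently discontinued patients to the same table. Its two columns are headed TD period 2 and TD period 3, with TD defined as study treatment discontinuation. The first row of the period 2 column reads "week 24 -week 40", every 4 weeks, 4 visits. The period 3 column starts at week 52.

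**Completers (Protocol Table 6-3).** The title is "Assessment schedule for study period 4 (safety follow-up period) for all patients", but its study-week rows cover completers only, for example "Study week for patients who completed period 2 treatment". It has no row for non-completers.

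**Entry into period 4 (Protocol Table 6-1, note 7).** A patient who discontinues early enters period 4 once the 199/TD visit is done. Section 5.6.2 wants that visit as soon as possible for a patient who leaves.

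**Frequency and length (Protocol 3.1 and 6).** Follow-up lasts at least 20 weeks from the last VAY736 dose, with visits every four weeks during the mandatory 20 weeks.

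**SAP 2.1.1.** For early stoppers in period 2, "EoT = the date of the last dose in period 2 plus 27 days". "The period 4 starts on the day after the end of treatment in period 2/3".

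**The concern.** A patient who takes one dose, has the discontinuation visit around week 4 and then leaves the treatment-period visits enters period 4 at about week 4. Table 5-3, the only schedule that section 5.6.2 names for this patient, has its first visit at week 28. That cannot be squared with four-weekly visits in the 20 weeks after last dose. The table appears to carry over an anchor that is right only for completers.

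What is at stake is scheduled laboratory monitoring after a B-cell depleting drug. Section 3.6 lists late onset neutropenia as a risk topic and promises regular IgG and IgM monitoring, and section 8.4 refers to close monitoring of neutrophil counts. Neutropenia and low IgG can be silent, so a missed blood draw is not replaced by spontaneous reporting. Section 5.6.2 also names persistent grade 3 neutropenia and serious or severe infection as reasons to consider stopping drug, so the group concerned may include patients who most need the checks.

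**Working it through.** **Inputs.** Doses are four-weekly; the last planned doses are at visits 106 and 207, weeks 20 and 48 (Protocol 5.5.4, Tables 6-1 and 6-2). Haematology and IgG are taken at the treatment-period visits, the TD visit and the period 4 visits (Tables 6-1 to 6-3).

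**Step 1: reproduce Table 5-3.** Visits per row = (end week − start week) / interval.
- Period 2: (40−24)/4 = 4; (56−40)/8 = 2; (80−56)/12 = 2; (128−80)/24 = 2. This matches the printed 4, 2, 2, 2.
- Visit weeks, period 2: 28, 32, 36, 40, 48, 56, 68, 80, 104, 128.
- Visit weeks, period 3 (same method from week 52): 56, 60, 64, 68, 76, 84, 96, 108, 132, 156.
- Both lists equal the completer rows of Table 6-3 at all ten visits.

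**Step 2: checks within 20 weeks of last dose.** Let L be the week of the last study-drug dose. Assume the TD visit is at L+4 and no other treatment-period visit follows. The checks in the window (L, L+20] are the TD visit plus the Table 5-3 visits at or before L+20. The gap to the next scheduled check is 28 − (L+4) in period 2 and 56 − (L+4) in period 3.

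| L | Window ends | Table 5-3 visits in window | Checks incl. TD | Gap (weeks) |
|---|---|---|---|---|
| 0 | 20 | none | 1 | 24 |
| 4 | 24 | none | 1 | 20 |
| 8 | 28 | 28 | 2 | 16 |
| 12 | 32 | 28, 32 | 3 | 12 |
| 16 | 36 | 28, 32, 36 | 4 | 8 |
| 20 (completer) | 40 | 28, 32, 36, 40 | 5 | 4 |
| 24 | 44 | none | 1 | 28 |
| 28 | 48 | none | 1 | 24 |
| 32 | 52 | none | 1 | 20 |
| 36 | 56 | 56 | 2 | 16 |
| 40 | 60 | 56, 60 | 3 | 12 |
| 44 | 64 | 56, 60, 64 | 4 | 8 |
| 48 (completer) | 68 | 56, 60, 64, 68 | 5 | 4 |

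**Step 3: patients who leave later.** With L = 0 and the last attended visit at week 8, 12, 16 or 20, the count is 2, 3, 4 or 5 of 5. For patients re-randomised from 300 mg to placebo, the last planned VAY736 dose is at week 20, so the window ends at week 40. Leaving after week 28, 32 or 36 gives 2, 3 or 4 of 5, and leaving at week 40 or later loses none.

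**Step 4: a relative anchor.** Set period 4 entry at L+4. Follow-up weeks 4, 8, 12 and 16 then fall at L+8, L+12, L+16 and L+20. With the check at L+4 that is 5 of 5 for every L. For L = 20 it returns 28, 32, 36, 40, the printed weeks.

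**The case against.** The best defence is that the weeks are nominal. Table 5-3 is titled an outline of visit frequency, its columns are headed TD, and Table 6-1 prints the TD visit in the same column as week 24. On that reading week 24 labels the TD visit, and a site following note 7 and the four-weekly rule would schedule correctly. Note 7 fixes entry into period 4, not the date of its first visit. This has some force. But no visible text says that the weeks should be shifted, and Table 6-3 and the note to Table 18-1 use the same numbers as actual study weeks for completers. A caveat remains: the text of notes 9 to 11 to Table 6-3 does not appear in the copy reviewed, and parts of the follow-up rules are redacted.

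It is also fair that the effect needs a patient who stops, leaves visits that remain open, accepts period 4 visits, and is at a site that applies the table literally. The TD visit, adverse event follow-up and SAE reporting continue.

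A reader might infer more than the documents support:
- *That the SAP contradicts the protocol schedule.* Its period definition assigns events to periods and is not a visit calendar. It supports a relative anchor, no more.
- *That results at FU Week 4 are pooled across very different times since last dose because of Table 5-3.* The pooling occurs anyway. A patient who stops after week 0 and attends through week 24 has visit 301 at week 28, 28 weeks after last dose. A 300 mg-to-placebo completer has it at week 56, 56 − 20 = 36 weeks after the last planned VAY736 dose.
- *That the table overruns the two-year limit.* The last visit falls 128 − L = 112 to 128 weeks after last dose for L = 16 to 0, but this also holds for discontinuers who attend through week 24, and 300 mg-to-placebo completers reach 156 − 20 = 136. The SAP rule, "Patients who have not yet recovered their B-cell counts two years after last VAY736 dosing, will be discharged from the study", caps the schedule in any case.
- *That the 20-week minimum in section 3.1 is breached.* The duration is met; it is the frequency within it that is not.

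**Conclusion.** The inconsistency is real but narrow. It sits within the protocol, between Table 5-3 on one side and Table 6-1 note 7 with sections 3.1 and 6 on the other, and it concerns only early stoppers who leave the treatment-period visits. In the worst case four of five scheduled checks in the 20 weeks after last dose are lost, and at the other end none. These counts rest on three assumptions: the site reads Table 5-3 literally, the TD visit falls 4 weeks after last dose, and no treatment-period visit follows it. The period 3 counts run from the last study-drug dose, so for patients switched to placebo the week 40 window in Step 3 applies instead.

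The documents give no number of affected patients; it is likely to be small. The week 24 primary analysis does not depend on this schedule. The point is worth correcting because the lost checks concern safety after B-cell depletion and the correction is cheap.

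**What to change.** In Table 5-3, and in one added non-completer row of Table 6-3, state the visits for patients who leave the treatment-period visits as follow-up weeks 4, 8, 12, 16, 24, 32, 44, 56, 80 and 104. Count them from last study-drug dose + 4 weeks, skip any already past when the patient leaves, and keep the existing two-year discharge rule. Anchoring on study drug rather than VAY736 lets sites that are blinded in period 3 apply it. Keep the study-week rows for completers and for discontinuers who attend through week 24 or 52.

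The cost is a small table edit and matching EDC visit scheduling at the next amendment. The number of planned visits stays at ten, and the SAP needs no change because its Table 5-1 already uses these follow-up weeks.

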5.6.3 Withdrawal of informed consent

Subjects may voluntarily withdraw consent to participate in the study for any reason at any time. Withdrawal of consent occurs only when a subject:

- Does not want to participate in the study anymore, and
- Does not allow further collection of personal data

In this situation, the investigator should make a reasonable effort (e.g. telephone, e-mail, letter) to understand the primary reason for the subject’s decision to withdraw his/her consent and record this information.

Study treatment must be discontinued and no further assessments conducted, and the data that would have been collected at subsequent visits will be considered missing.

Further attempts to contact the subject are not allowed unless safety findings require communicating or follow-up.

All efforts should be made to complete the assessments prior to study withdrawal. A final evaluation at the time of the subject’s study withdrawal should be made as detailed in the assessment table.

Novartis will continue to keep and use collected study information (including any data resulting from the analysis of a subject’s samples until their time of withdrawal) according to applicable law.

For US and Japan: All biological samples not yet analyzed at the time of withdrawal may still be used for further testing/analysis in accordance with the terms of this protocol and of the informed consent form.

For EU and RoW: All biological samples not yet analyzed at the time of withdrawal will no longer be used, unless permitted by applicable law. They will be stored according to applicable legal requirements.

5.6.4 Loss to follow-up

For patients whose status is unclear because they fail to appear for study visits without stating an intention to discontinue or withdraw, the investigator should show "due diligence" by documenting in the source documents steps taken to contact the patient, e.g., dates of telephone calls, registered letters, etc. A patient cannot be considered as lost to follow-up until the time point of his/her scheduled end of study visit has passed.

5.6.5 Early study termination by the sponsor

[figure not shown]
The study can be terminated by Novartis at any time for any reason. This may include reasons related to the benefit risk assessment of participating in the study, practical reasons, or for regulatory or medical reasons (including slow enrollment). Should this be necessary, the patient must be seen as soon as possible and treated as a prematurely withdrawn patient. The investigator may be informed of additional procedures to be followed in order to ensure that adequate consideration is given to the protection of the patient's interests. The investigator will be responsible for informing the Institutional Review Board/Independent Ethics Committee (IRBs/IECs) of the early termination of the trial.

6 Visit schedule and assessments

Table 6-1 lists all of the assessments and indicates with an "x" when the assessments are performed and should be documented in the eCRF. Assessments indicated with an "S" will only be documented at source.

Patients must be seen for all visits on the designated day, or as close to it as possible. Missed or rescheduled visits should not lead to automatic discontinuation. Patients who prematurely discontinue the study for any reason should be scheduled for a visit as soon as possible, at which time all of the assessments listed for the final visit will be performed. At this final visit, all dispensed investigational product should be reconciled and the adverse event and concomitant medications reconciled on the CRF.

In period 4, patients will have visits every four weeks for the mandatory 20-week safety follow-up period.

Patients who are not willing to return to the site for follow up visits in period 4, will be contacted for safety evaluations during the 30 days following the last administration of study treatment.

Table 6-1 Assessment schedule for period 1 (Screening) and period 2 (Randomized treatment period)

Period	Period 1: Screen	Period 2: Treatment					Notes
Visit	1 101 (BL)	102	103	104	105	106	199 / TD ⁷
Day	-28 1	28	56	84	112	140	168
Week	-4 0	4	8	12	16	20	24
Obtain informed consent (IC)	x						IC obtained prior to all study specific screening procedures
Demography	x						
Inclusion/exclusion	x	x					
Medical history	x						
Physical exam	S	S	S	S	S	S	
Height ¹ , weight, vital signs	x	x	x	x	x	x	1Height only collected at Screening
PhGA of overall disease activity	x	x	x	x	x	x	
ESSDAI	x	x	x	x	x	x	
Salivary flow, stimulated	x	x		x		x	
Salivary flow, [REDACTED]	x		x		x	x	
ECG	x	x				x	
Biopsy	X ²					X ^{2, 2A}	2Performing a biopsy for the substudy is optional at both screening and end of treatment ^{2A} Optional collection of archival tissue slides at end of treatment.
Randomization	S						
Pre-medication	x						
Dosage administration record	X ³	x	x	x	x		3First dose of study medication can be administered 1 calendar day after randomization
Contact IRT	S	S	S	S	S	S	4IRT will confirm if patient will be treated in period 3 but not notify whether patient was re-randomized

Period	Period 1: Screen	Period 2: Treatment						Notes
Visit	1 101 (BL)	102	103	104	105	106	199 / TD ⁷	7If patient discontinues treatment early, safety follow up period 4 will be entered after completion of this visit
Day	-28 -1	28	56	84	112	140	168	
Week	-4 0	4	8	12	16	20	24	
Adverse Events	x	x	x	x	x	x	x	AEs include both serious and non-serious events
Renal/liver event monitoring	x	x	x	x	x	x	x	
Prior concomitant medications/procedures	x	x						
Concomitant medications/procedures	x	x	x	x	x	x	x	
Period completion/disposition form	x						x	
ESSPRI	x	x	x	x	x	x	x	
FACIT-F, SF-36 PaGA of overall disease activity and patient diary ⁵		x	x	x	x	x	x	5Diary is to be completed weekly by patient
HIV, Hep B (HBsAg, anti-HBs, anti-HBc), Hep C	x							
TB (Quantiferon/PPD)	x							
Hematology and biochemistry	x	x	x	x	x	x	x	
Serum pregnancy	x	x	x	x	x	x	x	
Urinalysis	x	x	x	x	x	x	x	
IgG, IgM	x	x	x	x	x	x	x	
Pre-dose PK sample		x	x	x	x	x	x	
Immunogenicity		x			x		x	

Period	Period 1: Screen						Period 2: Treatment						Notes
	1	101 (BL)	102	103	104	105	106	199 / TD ⁷	7If patient discontinues treatment early, safety follow up period 4 will be entered after completion of this visit				
Visit	-28	1	28	56	84	112	140	168					
Day	-4	0	4	8	12	16	20	24					
Week													

TD = Study treatment discontinuation; If patient withdraws consent (as per definition) and will not enter period 4, assessments from Table 6-3 PSD must be performed as well

X = assessment to be recorded on clinical data base

S = assessment to be recorded on source documentation only

Table 6-2 Assessment schedule for study period 3 (Extended treatment period) only for patients who continue treatment

Period	Visit	Period 3: Extended Treatment								Notes
		201	202	203	204	205	206	207	208	
Day	168	196	224	252	280	308	336	339	364	
Week	24	28	32	36	40	44	48		52	
Physical exam		S	S	S	S	S	S		S	
Weight, vital signs		x	x	x	x	x	x		x	
PhGA of overall disease activity		x	x	x	x	x	x		x	
ESSDAI		x	x	x	x	x	x		x	
Salivary flow (stimulated and unstimulated)		x		x		x		x		
Saliva sample		x		x		x		x		
Local ECG			x					x		
Re-randomization		S ³								
Dosage administration record		x	x	x	x	x	x			
Pre-medication		x								
Contact IRT		S	S	S	S	S	S		S	
Adverse events		x	x	x	x	x	x		x	AEs include both serious and non-serious events
Renal/liver event monitoring		x	x	x	x	x	x		x	
Concomitant medications		x	x	x	x	x	x		x	
Period completion/disposition form										x
ESSPRI, FACIT-F, SF-36, PaGA, patient diary ⁴		x	x	x	x	x	x	x	x	4Diary is to be completed weekly by patient

³IRT will confirm if patient will be treated in period 3 but not notify whether patient was re-randomized

Re-randomization

Dosage administration record

Pre-medication

Contact IRT

Adverse events

Renal/liver event monitoring

Concomitant medications

Period completion/disposition form

ESSPRI, FACIT-F, SF-36, PaGA, patient diary⁴

Period	Period 3: Extended Treatment							Notes
	201	202	203	204	205	206	207	
Visit								
Day	168	196	224	252	280	308	336	364
Week	24	28	32	36	40	44	48	52
Hematology and biochemistry								
Serum pregnancy	x	x	x	x	x	x	x	x
Urinalysis	x	x	x	x	x	x	x	x
IgG, IgM	x	x	x	x	x	x	x	x
Pre-dose PK sample		x	x	x	x	x	x	
Post-dose PK sample							x	
Immunogenicity				x		x		

TD = Study treatment discontinuation; If patient withdraws consent (as per definition) and will not enter period 4, assessments from Table 6-3 PSD must be performed as well
 X = assessment to be recorded on clinical data base
 S = assessment to be recorded on source documentation only

Table 6-3 Assessment schedule for study period 4 (safety follow-up period) for all patients

Period 4: Follow-up	Mandatory follow-up visits	Conditional individualized follow-up visits	Mandatory	Notes
Visit	301 302	303 ⁹ 304	305 and 306 308 and 309	399 ¹⁰ / PSD/ (EoS)
Study week for patients who completed period 3 treatment	56 60	64 68	76 and 84 96 , 108¹² and 132	156 ¹¹ ¹² Marks the 1 year follow up time point
Study week for patients who completed period 2 treatment	28 32	36 40	48 and 56 68 , 80¹² and 104	128 ¹¹ ¹² Marks the 1 year follow up time point
Physical exam	S S	S S	S S	S S
Weight, vital signs	x x	x x	x x	x x
ESSDAI	x x	x x	x x	x x
Adverse events	x x	x x	x x	x x
Kidney and liver event monitoring	x x	x x	x x	x x
Concomitant medications	x x	x x	x x	x x
Period completion/disposition form				x
Hematology and biochemistry	x x	x x	x x	x x
IgG, IgM	x x	x x	x x	x x
Urine pregnancy ¹⁴	x x	x x	x x	x x
Serum pregnancy				x
Urinalysis	x x	x x	x x	x x
Lipid ⁸				x ⁸ Lipid is collected from same sample as chemistry
PK sample	x x	x x	x x	x* [*] Only for patients who prematurely withdraw

Period 4: Follow-up	Mandatory follow-up visits			Conditional individualized follow-up visits			Mandatory	Notes
Visit	301	302	303 ⁹	304	305 and 306	307, 308 and 309	399 ¹⁰ /PSD/ (EoS)	
Study week for patients who completed period 3 treatment	56	60	64	68	76 and 84	96, 108¹² and 132	156 ¹¹	¹² Marks the 1 year follow up time point
Study week for patients who completed period 2 treatment	28	32	36	40	48 and 56	68, 80¹² and 104	128 ¹¹	¹² Marks the 1 year follow up time point
Immunogenicity			x		x		x	

PSD = Premature subject/patient discontinuation; X = assessment to be recorded on clinical data base; S = assessment to be recorded on source documentation only

